#### Step Five

A covariate-adjusted estimate of the log hazard ratio  $\beta$  – call it  $\hat{b}$  – can then be obtained using weighted least squares methodology, by forcing the difference in means for the P covariates to zero, because under stratified randomization no differences between the stratification-adjusted means of the covariables are expected between the two treatment groups.

This translates to the following calculation for an estimate of *b*:

$$\hat{b} = \left(Z^T \left(V_f^T\right)^{-1} Z\right)^{-1} Z^T V_f^{-1} f$$

where  $Z = (1, \mathbf{0}_p^T)^T$ ,  $\mathbf{0}_p^T$  is a zero vector of length p, and, in terms of  $\hat{\beta}$ , is equivalent to:

$$\hat{b} = \hat{\beta} - V_{\hat{\beta}, \overline{g}}^T V_{\overline{g}}^{-1} \overline{g}$$

A consistent estimator for the variance of b is:

$$v_b = v_{\widehat{\beta}} - V_{\widehat{\beta},\overline{g}}^T V_{\overline{g}}^{-1} V_{\widehat{\beta},\overline{g}}$$
$$= \left( Z^T V_f^{-1} Z \right)^{-1}$$
(3)

The reportable values are the hazard ratio estimate,  $e^{\hat{b}}$ , along with its p-value and 95% confidence interval and  $\sqrt{v_b}$ , the standard error of the estimator for the log hazard ratio.

#### 8.2.1.1. Hypothesis Testing

The test statistic will be

$$Z = \frac{\hat{b}_{,}}{\sqrt{\nu_b}} \tag{4}$$

which under  $H_0$  has an asymptotic N(0, 1) distribution.

A test will be carried out at the 5% two-sided significance level with the following hypotheses:

$$H_0:\beta = 0$$
$$H_1:\beta \neq 0$$

and the p-value reported.

Here only a p-value favoring the RD-X19 treatment group will be flagged as statistically significant. This p-value corresponds to the primary analysis of the primary endpoint.

#### 8.2.1.2. CONFIDENCE INTERVAL

Under the assumption of a normal distribution for the log hazard ratio estimate,  $\hat{b}$ , a 95% confidence interval for the log hazard ratio will be calculated with limits given by:

$$\hat{b} \pm \Phi(0.975) \times \sqrt{\nu_b} \tag{5}$$

where  $\Phi(.)$  is the inverse cumulative density function for the standard normal distribution. A confidence interval for the hazard ratio will be generated by exponentiation of the limits of this confidence interval.

This confidence interval for the hazard ratio is a reportable value.

#### 8.2.1.3. DEFINITIONS OF BASELINE COVARIATES AND IMPUTATION OF MISSING VALUES FOR THESE COVARIATES

Nasopharyngeal viral load numerical values (copies/mL) are recorded at baseline. For the viral load quantitation assay, the specified lower limit of quantification (LLOQ) and limit of detection (LOD) are both 5.0 x  $10^2$  copies/mL (which is 2.6990 on the Log10 scale) and the upper limit of quantification (ULOQ) is  $5.0 \times 10^8$  copies/mL (which is 8.6990 on the Log10 scale). Most subjects are expected to have a numerical value between LLOQ and ULOQ. Although the specified LOD and LLOQ for this specific PCR assay are equal ( $5.0 \times 10^2$  copies/mL), it is possible for a sample to have result "Detected, but below the LLOQ" if the amount of viral RNA in the sample is less than the LOD (the minimum concentration at which viral RNA can be reliably detected). Subjects with a recorded value of "Not detected" (which corresponds to a value below the LOD) or "Detected, but below the LLOQ" will be assigned a value equal to half the LLOQ, i.e.,  $2.5 \times 10^2$  copies/mL (which is 2.3979 on the Log10 scale). Similarly, any subjects with "Detected" and noted to be "above ULOQ" will be assigned a value equal to twice the ULOQ, i.e.,  $1.0 \times 10^9$  copies/mL (which is 9.0 on the Log10 scale).

The first covariate is Baseline Log10 nasopharyngeal viral load numerical values and so all numerical values will be in the range 2.3979 to 9.0. If at baseline the assay is not carried out, then prior to imputation the value of nasopharyngeal viral load will be set to missing.

Ethnicity is recorded at baseline as "Hispanic or Latino", "Non-Hispanic or Latino", "Not Reported", or "Unknown". The Ethnicity covariate will assign a value 0 to "Hispanic or Latino" and assign a value 1 to "Non-Hispanic or Latino". For other categories (prior to imputation) the numerical value for the Ethnicity covariate will be set to missing.

Hours since onset of symptoms is determined by subtracting the time/date of onset of symptoms from the time/date of screening. If either date is missing then prior to imputation the numerical value for the Hours since onset of symptoms covariate will be set to missing.

Baseline Risk Factor Score (BRFS) is a numerical score that considers 12 individual risk factors for progression. Each individual risk factor contributes 0 to the BRFS if not present and contributes a value of either 1 or 2 (as specified below) if the individual risk factor is present at baseline (but each medical history risk factor will contribute zero if the condition is not ongoing at baseline).

The following factors if present at baseline will contribute 1 to the BRFS: Age  $\geq$ 65, Chronic Liver or Kidney Disease, Asthma, COPD, Cystic Fibrosis, Diabetes (type I or type II), Heart Disease, Hypertension, Immune Deficiency (including HIV), Cerebrovascular Disease (Stroke). For Overweight/Obesity, Overweight (BMI  $\geq$ 25.0 to <30) will contribute a score of 1 and Obesity (BMI  $\geq$ 30) will contribute a score of 2. For Smoking Status: (i) a Current Smoker will contribute a score of 2; (ii) a Former Smoker who stopped smoking  $\leq$ 2 years ago will also contribute a score of 2; (iii) a Former Smoker who stopped smoking >2 but  $\leq$ 10 years ago will contribute a score of 1; and (iv) a Former Smoker who stopped smoking >10 years ago will contribute a score of 0.

The BRFS covariate will be treated as a continuous variable, but the total score for an individual subject will be capped at  $BRFS_{CAP}$  in order to avoid the undue influence in the NPANCOVA analysis of a few subjects with a very high score. The value of  $BRFS_{CAP}$  will be set at 6 provided that the proportion of subjects with  $BRFS \ge 6$  is no more than 0.10. If not, then successively higher integer values for  $BRFS_{CAP}$  will be considered until the proportion of subjects with  $BRFS \ge BRFS_{CAP}$  is no more than 0.10.

- Note: At baseline the CRF captures specifically Age, BMI, Smoking status, and History of Asthma (with a field for whether or not it is ongoing). The CRF also captures all other medical History conditions/disorders as a text field and whether or not the subject separately for each of the eight specific factors (Chronic Liver or Kidney Disease, COPD, Cystic Fibrosis, Diabetes [type I or type II], Heart Disease, Hypertension, Immune Deficiency (including HIV), Cerebrovascular Disease [Stroke]) has the condition/disorder will be determined by manual review (prior to unblinding) of a list of those conditions/disorders that are ongoing at baseline.
- Note: Only if the Medical History page is completely missing for a subject will the Baseline Risk Factor Score be considered (prior to imputation) to be missing.

Missing data for each of the covariates will be imputed as follows: For a given covariate the mean value of the non-missing values (for both treatment groups combined) in each of the 4 strata will be determined. Then subjects in stratum h with missing values for the covariate will be replaced by this mean of the non-missing values from stratum h.

#### 8.2.1.4 DEGREE OF IMBALANCE AMONG THE COVARIATES

The (scalar) quantity  $Q_0$  is determined to evaluate the extent of the random imbalances between the treatment groups and is defined by:

$$Q_0 = (\boldsymbol{f} - \boldsymbol{Z}\boldsymbol{b})^T \boldsymbol{V}_{\boldsymbol{f}}^{-1} (\boldsymbol{f} - \boldsymbol{Z}\boldsymbol{b})$$

It has an approximate  $X^2$  distribution with 4 degrees of freedom. The value of  $Q_0$  will be calculated, compared to the appropriate  $X^2$  distribution, and a p-value calculated.

Note: The criterion is not a test for validity of NPANCOVA, but due to the stratified randomization requirement of the methodology small p-values for  $Q_0$  should just be interpreted as a chance finding.

### 8.2.2. KAPLAN-MEIER ANALYSIS

This analysis will be carried out on the FAS population. The non-parametric Kaplan-Meier method will be used to estimate the survival curves. The plot will show the number of subjects at risk on the time axis, and the y-axis will indicate the success probability.

The median survival time will also be estimated for each treatment group (these medians will also be superimposed on the plot), together with its 95% CI using the Brookmeyer & Crowley method [13] (using the "log-log" transformation option). Estimates of the 25th and 75th percentiles and the median will be derived, along with their corresponding 95% CIs, and reported in a table.

#### 8.2.3. COX PROPORTIONAL HAZARDS (PH) ANALYSIS

A secondary analysis will be carried out on the FAS for the primary endpoint based on a stratified Cox PH model [14], using Efron's method for handling ties [9]. As for the primary analysis the Cox PH model will have RD-X19 as the reference. This analysis will use the same strata as the primary analysis. The same covariates for which the NPANCOVA analysis adjusted will also be incorporated into the Cox PH model (as covariates).

Only the (conditional) hazard ratio and its 95% confidence interval will be reported, along with its associated p-value. These quantities will be reported on the identity scale, i.e. they will be exponentiated before reporting. The covariates adjusted for will be specified in the table as a footnote.

#### 8.2.4. SUPPORTIVE ANALYSIS

NPANCOVA, Kaplan-Meier and Cox PH supportive analyses of the primary endpoint will be carried out for the PP population.

#### 8.2.5. FURTHER SECONDARY AND SENSITIVITY ANALYSES

A secondary analysis based on NPANCOVA will be carried out for the primary endpoint excluding the FAS subjects that were qPCR negative at baseline.

A sensitivity analysis based on NPANCOVA in the FAS will be carried out for the primary endpoint in which the following rules for event times and censoring will be implemented:

- Subjects that are hospitalized, who progress to more severe forms of COVID-19, or who require therapy with an FDA-authorized COVID-19 treatment will be censored at 360 hours (which corresponds to the end of the time window for the day 14 visit). This rule takes precedence over all other rules.
- II. A subject that records "SSSSS" i.e., five consecutive timepoints (corresponding to an approximately 48-hour period) at which the signs and symptoms have resolved who does not have any subsequent symptom recurrence or subsequent disease progression during the subject's remaining time on study, will have the event at the time of the first "S" in this sequence.
- III. Subjects not satisfying case (i) or (ii) will be censored at the last time that they have ediary data recorded.

Counts and percentages will be provided for subjects in each of cases (I), (II), and (III), as defined above. In addition, counts and percentages will be provided separately for subjects hospitalized, subjects who progress to more severe forms of COVID-19, and subjects who require therapy with an FDA-authorized COVID-19 treatment.

#### 8.2.6. SUBGROUP ANALYSES

For the primary endpoint in the FAS an unstratified Cox PH model with a single term for treatment will be used to derive the hazard ratio and its 95% confidence interval for each of the following subgroups:

- 1. Region (West, South-East, North-East/Mid-West)
- Hours at screening since onset of first COVID-19 sign or symptoms (≤24, >24-≤48, >48-≤72)
- 3. Previous COVID-19 diagnosis via FDA-approved diagnostic test (yes, no)
- 4. Prior COVID-19 vaccination (yes, no)
- 5. SARS-Cov-2 rapid antigen test type (Flowflex, BinaxNOW)
- 6. Age category (40-49, ≥50)
- 7. Sex (male, female)
- 8. Race (White, Black/African American, Other races combined)
- 9. Ethnicity (Hispanic or Latino, not Hispanic or Latino)
- 10. Total baseline disease severity score (<1.25, ≥1.25)
- 11. Baseline Log10 Nasopharyngeal Viral Load (≤median value, > median value)
- 12. Baseline Risk Factor Score (0-2, ≥3)

The study is powered on the basis of the overall treatment effect and is not designed to have high power for separate subgroup analyses.

The regions are defined as follows: (a) West consists of sites in Arizona, California, Nebraska, Nevada, Texas, Utah; (b) South-East consists of sites in Florida, Georgia, Louisiana, Mississippi, North Carolina, Tennessee; and (c) North-East/Mid-West consists of sites in Iowa, Illinois, Kentucky, Massachusetts, Maryland, Michigan, Missouri, New York, and Ohio).

For the subgroup analysis by race subjects with two or more races recorded will be included in the category "Other races combined", except for subjects reporting two races of "Black" and "African American" who will be included in the "Black/African American" category.

For the subgroup analysis by Baseline Log10 Nasopharyngeal Viral Load, the data will first be transformed as described in the first paragraph of Section 8.2.1.3, so that all non-missing values will be in the range 2.3979 to 9.0.

For the above subgroup analyses the following categories (all of which are expected to have very few if any subjects) will not be included: unknown, inconclusive, missing, not reported, undifferentiated (for gender only), and >72 hours (for hours since symptom onset only).

#### 8.2.7. EXPLORATORY ANALYSES

Exploratory analyses of sign or symptom resolution by type of sign or symptom will be carried out as follows:

For each FAS subject separately for each symptom that is moderate or greater at baseline, the time to the first of five consecutive timepoints at which that symptom is resolved (to become mild or not present) will be determined. If this has not occurred, then the subject for this symptom will be censored at the last time that they have e-diary data recorded.

Similarly, for each FAS subject that has fever (temperature  $\geq 100.5$  °F) at baseline, the time to the first of five consecutive timepoints at which that sign is resolved (to become < 100.5 °F) will be determined. If this has not occurred, then the subject for this sign will be censored at the last time that they have e-diary data recorded.

For each treatment group Kaplan-Meier estimates of the median time to initial symptom resolution, together with its 95% CI, will be derived separately for each sign or symptom. For each treatment group baseline counts and percentages will also be provided separately for each sign or symptom.

## 8.3. KEY SECONDARY ENDPOINT

All analyses of the key secondary endpoint will be carried out only after implementing all data handling rules described in Section 4.2.

#### 8.3.1. RULES FOR EVENT TIMES AND CENSORING

The following rules for event times and censoring will be implemented in the analysis of the key secondary endpoint:

- Subjects that are hospitalized, who progress to more severe forms of COVID-19 or who require therapy with an FDA-authorized COVID-19 treatment will be censored at 360 hours (which corresponds to the end of the time window for the Day 14 visit). This rule takes precedence over all other rules.
- A subject that records "NN" based on two tests at least six hours apart without subsequent rebound during the subject's remaining time on study will have the event at the time of the first "N" in this sequence, and
- iii. Subjects not satisfying case (i) or (ii) will be censored at the time of their last selfassessment /diagnostic test.
- Note: Case (iii) subjects with no SARS-CoV-2 antigen tests after randomization will be censored at time zero.

The event times and censoring status will be listed.

#### 8.3.2. ANALYSIS

The analysis of the key secondary endpoint will be based on the FAS and the same as that for the primary endpoint (primary: NPANCOVA, secondary: Kaplan-Meier and Cox PH analyses), using the same method for handling ties, the same stratification factors, and with the same pre-specified prognostic baseline covariates as included in the primary analysis of the primary endpoint. Counts and percentages will be provided in the tables reporting NPANCOVA analyses for subjects in each of cases (i), (ii), and (iii), as defined in Section 8.3.1. In addition, counts and percentages will be provided separately for subjects hospitalized, subjects who progress to more severe forms of COVID-19, and subjects who require therapy with an FDA-authorized COVID-19 treatment.

Supportive analyses (NPANCOVA, Kaplan-Meier, and Cox PH analyses) of the key secondary endpoint will be carried out for the PP population. A secondary analysis based on NPANCOVA will be carried out for the key secondary endpoint excluding the FAS subjects that were qPCR negative at baseline. Subgroup analyses based on the FAS will also be provided for the key secondary endpoint by SARS-Cov-2 rapid antigen test type (Flowflex, BinaxNOW). This subgroup analysis will be based on an unstratified Cox PH model with a single term for treatment from which the hazard ratio and its 95% confidence interval will be derived for each of the two categories of this subgroup.

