The second step is to identify cases that are counted as subsequent virological rebound which is defined as "having two or more positive tests out of three consecutive assessments". This would include "PPP", "PPN", "PNP", "NPP", or "PP". In addition, if a "P" is followed by an "M" or "I" then the "P" will be carried forward so that this will also be counted as a rebound.

The key secondary endpoint is then calculated as time to first of two consecutive negative SARS-CoV-2 antigen tests (with a minimum time between tests of 6 hours) without subsequent virological rebound, during the subjects' remaining time on study. Subsequent virological rebound is defined as having two or more positive tests out of three consecutive assessments.

The following rules for event times and censoring of the key secondary endpoint will be implemented:

(i) Subjects that are hospitalized, who progress to more severe forms of COVID-19, or who require therapy with an FDA-authorized COVID-19 treatment will be censored at 360 hours (which corresponds to the end of the time window for the Day 14 visit) and this rule takes precedence over all other rules;

(ii) A subject that records "NN" based on two tests at least six hours apart without subsequent rebound during the subject's remaining time on study will have the event at the time of the first "N" in

Confidential Information; this Protocol is Confidential and Proprietary to EmitBio Inc.

this sequence, and

(iii) Subjects not satisfying case (i) or (ii) will be censored at the time of their last self-assessment /diagnostic test.

The primary analysis of this key secondary endpoint will be nonparametric randomization-based covariate adjustment for time-to-event outcomes using Efron's method for handling ties, with stratification by the design's stratifications factors, and with the same 1-4 pre-specified prognostic baseline covariates as included in the primary analysis of the primary endpoint. The 95 % two-sided CI for the hazard ratio will also be derived. The primary analysis will be based on the FAS. In addition, the same Kaplan-Meier-based analyses as described for the primary endpoint will also be provided for this key secondary endpoint.

A secondary analysis of this key secondary endpoint will be carried out on the FAS based on a Cox Proportional Hazards model, using Efron's method for handling ties, including the same stratification factors and covariates as included in the primary analysis of this endpoint.

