#### 3.2. STUDY DESIGN

This is a randomized, double blind, sham controlled study of the EmitBio RD-X19 light dosing treatment device. 326 subjects will be randomized at a 1:1 ratio into RD-X19 treatment and sham device treatment groups.

Subjects will be aged 40-years-old or over on the date of enrollment, have a positive COVID-19 test with time since symptom onset of 72 hours or less, and meet the NIH and FDA definition of mild COVID-19. For randomization, subjects will be stratified by age (categories 40-49 years and  $\geq$ 50 years) and baseline disease severity score (< 1.25,  $\geq$  1.25).

Subjects will be treated for 7 days and followed up for a further 7 days after the end of treatment (i.e., subjects will spend 14 days on the study in total).

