### 4.2. KEY SECONDARY ENDPOINT

Note that at each of the twice-daily assessment times at which the subject is scheduled to take the SARS-CoV-2 antigen test, the results will be either Negative (N), Positive (P), Inconclusive (I), or Missing (M).

The key secondary endpoint is the **time to first of two consecutive negative SARS-CoV-2 antigen tests** (with a minimum time between tests of 6 hours) without subsequent virological rebound during the subject's remaining time on study. It is measured in hours from the time of randomization to the time of the first of two consecutive negative tests.

The following sequences will be counted as satisfying this condition of having "two consecutive negative SARS-CoV-2 antigen tests":

- a) "NN" and the two tests are at least six hours apart.
- b) More than two consecutive "N" values where the first and last are at least six hours apart.
- c) "N" followed by at most three "M" or "I" values, followed by "N" where the two "N" values are at least six hours apart.

In the remainder of the SAP the use of "NN" will refer to any of cases (a)-(c).

Note: Only tests taking place after the time of randomization are considered when determining if the key secondary endpoint has been met.

**Subsequent virological rebound** is defined as having two or more positive tests out of three consecutive assessments. In addition to "PP", the following test result patterns, seen after one of (a) to (c) above, will be sufficient to define subsequent virological rebound:

- i. "PPP"
- ii. "PPN"
- iii. "PNP"
- iv. "NPP"

Note: If a "P" is followed by an "M" or "I" then the "P" will be carried forward so that this will also be counted as a subsequent virological rebound.

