# 7.6. BASELINE COVID-19-RELATED INFORMATION AND OTHER BACKGROUND CHARACTERISTICS

The following variables will be summarised in tables for the FAS.

- Result of baseline SARS-Cov-2 antigen test (positive, negative, inconclusive)
- SARS-Cov-2 antigen test type (Flowflex, BinaxNOW)
- o Result of flu A rapid antigen test (positive, negative, invalid)
- Result of flu B rapid antigen test (positive, negative, invalid)
- Randomization Stratum (age 40-49, Disease Severity Score < 1.25; age 40-49, Disease Severity Score ≥ 1.25; age ≥50, Disease Severity Score < 1.25; age ≥50, Disease Severity Score ≥ 1.25)

- Total baseline disease severity score (continuous variable)
- Total baseline disease severity score (<1.0,  $\geq$ 1.0-<1.25,  $\geq$ 1.25-<1.75,  $\geq$ 1.75)
- Baseline individual self-assessed symptom scores:

- Cough (0,1,2,3)
- Sore throat (0,1,2,3)
- Nasal congestion (0,1,2,3)
- Headache (0,1,2,3)
- Chills or sweats (0,1,2,3)
- Myalgia (0,1,2,3)
- Fatigue (0,1,2,3)
- Nausea, with or without vomiting (0,1,2,3)
- Loss of taste (yes, no)
- Loss of smell (yes, no)
- Baseline oral temperature (continuous variable)
- o Baseline oral temperature (<100.5, ≥100.5 °F)
- Baseline heart rate beats/min (continuous variable)
- Baseline heart rate (<70, ≥70-<80, ≥80-<90, ≥90)

- Systolic blood pressure (mmHg)
- Diastolic blood pressure (mmHg)
- Oxygen saturation at rest (%)
- Respiratory rate at rest (continuous variable)
- o Respiratory rate at rest (<20, ≥20 breaths/min)
- Oxygen saturation from Dyspnea on exertion assessment (%)
- Respiratory rate from Dyspnea on exertion assessment (continuous variable)
- Respiratory rate ≥20 and Oxygen saturation <96% from Dyspnea on exertion assessment (yes, no)
- Hours at screening since onset of first COVID-19 sign or symptoms (continuous variable)
- Hours at screening since onset of first COVID-19 sign or symptoms ( $\leq 24$ ,  $>24-\leq 48$ ,  $>48-\leq 72$ , >72)
- Baseline Risk Factor Score (as defined in Section 8.2.1.3)
- Baseline Log10 Nasopharyngeal Viral Load category (Not Detected or Below LLOQ; Above ULOQ; Numerical value between LLOQ and ULOQ, missing)
- Baseline Log10 Nasopharyngeal Viral Load (summary statistics [copies/mL] for numerical value between LLOQ and ULOQ)

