#### Step Three

The method requires within-strata randomisation with regards to treatment allocation. In the present case there are four strata, corresponding to the crossing of two binary covariates: age (40-49 or  $\geq$  50) and baseline disease severity score (< 1.25 or  $\geq$  1.25). These will be coded as follows:

Stratum subscript (h)	Stratum
1	40-49, < 1.25
2	40-49, ≥ 1.25
3	≥ 50, < 1.25
4	≥ 50, ≥ 1.25

Furthermore, 1 will refer to the RD-X19 treatment group and 2 the Sham treatment group. So, for example, those in the RD-X19 treatment group within stratum  $\geq$  50, < 1.25 will have subscript '31' i.e., subject *j* in this stratum will have covariate vector  $\mathbf{x}_{31j}$ ; those in stratum 40-49, < 1.25 in the Sham treatment group will have subscript '12' i.e., subject *j* in this stratum will have covariate vector  $\mathbf{x}_{12j}$ .

NPANCOVA adjusts an initial estimate of the log hazard ratio (resulting from a treatment-only Cox proportional hazards model as in Step One) for covariates in a nonparametric manner. In this case, covariates are prognostic baseline covariates chosen to improve precision of the estimate of the log hazard ratio. Those covariates are:

- o Baseline Log10 nasopharyngeal viral load
- o Ethnicity
- Hours since onset of symptoms
- o Baseline Risk Factor Score (BRFS).

Further details on the definitions and numerical values for these baseline covariates and imputation of their missing values is described in Section 8.2.1.3. These covariates will be indexed as follows:

Index	Covariate
1	Baseline Log10 nasopharyngeal viral
	load
2	Ethnicity

3	Hours since onset of symptoms
4	Baseline Risk Factor Score

So, letting  $x_{hij}$  be the  $p \times 1$  vector of covariates (p is the number of covariates) for the *jth* individual in treatment group i from stratum h, in  $x_{hij}$  the first element will be their baseline Log10 nasopharyngeal viral load value, the second element will be their Ethnicity value, etc.

 $X_{hi}^{T} = (\mathbf{x}_{hi1}, \mathbf{x}_{hi2}, \mathbf{x}_{hi3}, \dots, \mathbf{x}_{hin_{hi}})$  is a  $p \times n_{hi}$  matrix containing the covariate information for the subjects in stratum h in treatment group i.

The  $p \times 1$  vector of covariate means in stratum h, treatment group i is given by:

$$\overline{\boldsymbol{x}}_{hi} = \frac{\sum_{j=1}^{n_{hi}} \boldsymbol{x}_{hij}}{n_{hi}}$$

and we define the  $n_{hi} \times p$  matrix:

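### The formally tested key secondary analysis does not adjust for antigen test type, which forgoes a cheap gain in precision on an endpoint read from that test

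*SAP*

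**What the plan says.** - **Endpoint.** SAP 4.2 defines the key secondary endpoint as "time to first of two consecutive negative SARS-CoV-2 antigen tests", without later rebound. It is timed from randomization and counts only tests taken after randomization.
- **Covariates.** SAP 8.2.1, Step Three, lists baseline log10 nasopharyngeal viral load, ethnicity, hours since symptom onset and Baseline Risk Factor Score. It gives their purpose: "covariates are prognostic baseline covariates chosen to improve precision of the estimate of the log hazard ratio". SAP 8.3.2 carries them over "with the same pre-specified prognostic baseline covariates as included in the primary analysis of the primary endpoint". Protocol 9.4.1 requires this: "with the same 1-4 pre-specified prognostic baseline covariates as included in the primary analysis of the primary endpoint".
- **Strata.** SAP 3.2: "For randomization, subjects will be stratified by age (categories 40-49 years and" 50 and over) and by baseline severity score. Test type is not a factor.
- **Test type.** SAP 7.6 tabulates "SARS-Cov-2 antigen test type (Flowflex, BinaxNOW") directly after the baseline antigen result. In SAP 8.3.2 its only use is: "Subgroup analyses based on the FAS will also be provided for the key secondary endpoint by SARS-Cov-2 rapid antigen test type (Flowflex, BinaxNOW"), fitted with an "unstratified Cox PH model with a single term for treatment".
- **Testing order.** Under SAP 8.3.3 the key secondary is tested only if the primary is significant. No power, event count or effect size is stated for it.

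**The concern.** For symptom resolution, the antigen kit has no direct part in the outcome. For the key secondary endpoint, the kit is how the outcome is read. If one brand stays positive longer at the same viral level, times to negative differ by brand for reasons unrelated to treatment. That spread goes into the standard error of the formal test unless the model accounts for it. Randomization does not balance brand by design, so a chance imbalance between arms would also move the estimate somewhat.

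By the SAP's own criterion (a baseline value, prognostic, improving precision), test type is a natural candidate for this endpoint. The within-brand subgroup models do not replace adjustment. They drop the strata and covariates, split the sample, and give no pooled brand-adjusted estimate. If the subgroup results look uneven after unblinding, any brand adjustment made then would be post hoc.

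**Working it through.** **1. The plan's own figure.** The only sample-size figure is for the primary endpoint. Schoenfeld events = 4 × (1.960 + 1.645)² / (ln 0.62)² = 4 × 12.99 / 0.2285 = 227.5, which rounds up to the stated 228. Expected events are 163 × 0.9 + 163 × 0.5 = 228.2. Both reproduce. There is no corresponding figure for the key secondary.

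**2. What a further covariate does in the planned method.** SAP 8.2.1, Step Five, gives v_b = v_β − V′ V_g⁻¹ V, where V is the covariance of the log hazard ratio with the covariate mean differences and V_g is the covariance matrix of those differences. A prognostic covariate enlarges the subtracted term and so lowers v_b. A covariate unrelated to outcome leaves v_b almost unchanged.

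**3. Assumptions.** The documents give no brand effect, no brand split and no antigen-clearance rates. The following are assumed:
- n = 326, allocated 1:1
- exponential times with a sham median of 170 h (close to the 170.3 h in Protocol Table 1, but that is symptom resolution in sham subjects aged 40-49)
- a brand effect on the hazard of a negative test of 1.25, 1.5 or 2.0

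**4. Validity, using a simple test.** Log-rank ignoring brand was compared with log-rank stratified by brand: 8,000 runs per setting, censoring at 360 h, treatment effect 1/0.69 on the hazard of a negative test.

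| Split | Brand effect | Power, brand ignored | Power, stratified by brand | Difference (points, unrounded inputs) |
|---|---|---|---|---|
| 50/50 | 1.0 | 86.3% | 86.0% | −0.3 |
| 50/50 | 1.25 | 86.1% | 86.3% | +0.2 |
| 50/50 | 1.5 | 85.7% | 87.6% | +1.9 |
| 50/50 | 2.0 | 83.3% | 88.7% | +5.4 |
| 20/80 | 1.0 | 86.6% | 86.3% | −0.3 |
| 20/80 | 1.25 | 85.9% | 86.0% | +0.1 |
| 20/80 | 1.5 | 85.8% | 86.6% | +0.7 |
| 20/80 | 2.0 | 84.2% | 86.9% | +2.7 |

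Under no treatment effect, one-sided rejection was 2.2% to 2.8% throughout, with or without brand, against a nominal 2.5%.

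**5. Chance imbalance.** With a 50/50 split, the 95% limit for the difference in brand share between arms is 1.96 × √(2 × 0.5 × 0.5 / 163) = 0.109, about 11 percentage points. The approximate factor on the unadjusted hazard ratio, taking 0.108, is:
- 1.25^0.108 = 1.02
- 1.5^0.108 = 1.04
- 2^0.108 = 1.08

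**6. Size in the planned test.** NPANCOVA was simulated as in SAP 8.2.1 with the four strata and viral load already adjusted, treatment HR 0.70, follow-up to 336 h and brand share 30% or 50%. There were two sets of runs, with 2,000 and 3,000 trials per setting. The second coded the brand effect as its reciprocal (0.8, 0.67, 0.5). Combined ranges for adding brand:

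| Brand effect | Gain in z-squared | Gain in power (points) |
|---|---|---|
| 1.0 | – | within 0.2 of zero |
| 1.25 | about 1% | 0.1 to 1 |
| 1.5 | 3% to 4% | 0.7 to 1 |
| 2.0 | 7% to 10% | 2 to 4 |

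Null rejection was about the same with and without brand. At a brand effect of 2.0, the two analyses disagreed on significance in about 8% of trials.

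**The case against.** The strongest reply is that nothing is invalid. Leaving out a prognostic covariate does not bias a randomized test, and any unadjusted baseline variable can be imbalanced by chance. The SAP also follows Protocol 9.4.1, which caps the covariates at four and requires the same set for both endpoints. Two of the four, viral load and hours since onset, bear directly on antigen clearance. Brand is tabulated by arm, and a within-brand hazard ratio cannot be confounded by brand imbalance. All of this stands, and it limits the point to precision and robustness.

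Two further objections also stand:
- **Which kit is recorded.** SAP 7.6 lists test type beside the baseline result, yet the endpoint uses only post-randomization tests, mostly read from kits given out on Day 1 (Protocol 8.3). Neither document says that home kits match the baseline brand or that a subject keeps one brand throughout. A reader might infer that the recorded brand is the measuring instrument for every endpoint test; the documents do not establish that.
- **What the subgroup shows.** A reader might take the brand subgroup as an admission that brand drives this endpoint. It does not show that, because SAP 8.2.6 plans the same subgroup for the symptom endpoint.

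The objection does not explain why a value already collected, and a plausible source of variation in this endpoint, should appear only in subgroup models that give no pooled adjusted estimate.

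**Conclusion.** The point holds as a low-cost improvement to the analysis of the key secondary endpoint. Adding test type would be expected to gain about 1% to 10% in z-squared and about 0 to 4 points of power if the brand effect lies between 1.25 and 2.0. It would cost essentially nothing if the brands do not differ. A gain above about 1 point needs a brand effect stronger than 1.5, and the documents contain no evidence on its size.

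Two stronger readings are not supported. The omission does not inflate type I error, as the null simulations show. Nor should the gain be put at 5 to 6 points. Figures of that size come from a brand-stratified log-rank test (up to 5.4) or a Cox model (up to 6), whereas the formal test is NPANCOVA, which targets a population-averaged log hazard ratio. All sizes rest on the assumed clearance times, brand effects and splits listed above.

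**What to change.** Before unblinding (SAP 2.1 allows amendments until database lock), amend SAP 8.3.2:

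1. Add antigen test type, coded 0/1, as a further covariate in the key secondary NPANCOVA and Cox models only. Impute missing values by stratum mean as in SAP 8.2.1.3, and refer Q0 for this analysis to 5 degrees of freedom.
2. Define the variable as the brand of the kit dispensed for the twice-daily post-randomization tests, or as the baseline brand if the same brand is used throughout.
3. Document the departure from the shared set of one to four covariates in Protocol 9.4.1.

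If the sponsor prefers to keep the protocol's covariate set for the formal test, pre-specify the brand-adjusted NPANCOVA as a sensitivity analysis of the key secondary endpoint, with the same definition of test type.

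The primary endpoint analysis is unchanged. The cost is one degree of freedom, a short SAP amendment and, under the first option, a small documented departure from the protocol's covariate list.
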